### 5.5 Strategies for Recruitment and Retention

1. Our target sample size includes 80 adolescents ages 12-17 of any sex, race and ethnicity. Based on the percentage of eligible participants in previous studies with similar criteria, we anticipate that we will need to screen 100 participants in order to reach our target sample size of 80 adolescents.

a. Regarding the NIH Policy and Guidelines on The Inclusion of Women and Minorities as Subjects in Clinical Research:

i. Our sample will include female children/adolescents and mothers or female caregivers. We anticipate a large proportion of child and caregiver participants to be female – in previous studies with a similar population, 74% of child participants and 90% of parent participants were female.

ii. Our sample will include minorities. Specifically, we estimate enrolling participants at the following rate: 11.0% Hispanic/Latino and 89.0% not Hispanic/Latino. In terms of racial categories, we expect to enroll participants in the following proportions: 78.4% White, 7.0% Asian, 4.0% More than One Race, 9.0% Black or African American, 1.4% American Indian/Alaska Native, and 0.2% Native Hawaiian or Other Pacific Islander. Referrals will come from the Seattle Children's Pain Clinic.

iii. Participants will be recruited via referral from providers at Seattle Children's Pain Clinic and via EMR review. Health care providers will inform patients and families about the study and provide families with study information in the form of a flyer. Providers will then ask families if they are willing to be contacted by research staff to assess interest in the study and discuss participation. The provider will refer interested, potentially eligible participants by entering participant and parent names and contact information into a secure REDCap database hosted at SCH, or may send the referral by secure fax, email, or voicemail. Families who do not give permission for their information to be shared with SCH by the referral site may still contact SCH staff or submit their information to SCH via a secure link on the study website (self-referral), or via email or secure voicemail.

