**Self-management processes.** Using Common Data Elements for Self-Management, 3 self-management processes will be assessed. Pain self-efficacy. The Pain Self-Efficacy Scale (45) is a 7-item measure that assesses the child's beliefs in carrying out activities when in pain. The scale has demonstrated good internal consistency, cross-informant reliability with parent report, and strong construct validity. Patient activation. The Patient Activation Measure (46) is a 13-item questionnaire that assesses an individual's knowledge, skill and confidence for managing their health and health care. The PAM uses a 0-100 scale resulting in 4 levels of activation, from low (1) to high (4). The measure is not disease specific, and has been successfully used with a wide variety of chronic conditions. Although developed for adults, the PAM has been used in children ages 12 and above, is reliable, and shows strong construct validity. Self-management skills. The Transition Readiness Assessment Questionnaire 3.0 (47) is a 14-item measure that assesses self-management skills related to healthcare interactions, self-advocacy, and decision-making. The TRAQ has been validated in children 12-18 years with a broad range of health conditions, has good reliability and strong construct validity.

**Pain and Health Outcome Measures.** We will measure daytime function and health outcomes using well-validated instruments. WebMAP has diary assessments programmed into the web site to prospectively collect pain intensity and pain-related disability data over 7-day periods. Child pain intensity will be rated on the online diary using an 11-point NRS (50). The CALI is a validated instrument of pain-related disability measured by youth difficulty in performing usual daily physical, social, and recreational activities (e.g., going to school, running, walking) due to pain (51). We will measure fatigue using the PedsQL Multidimensional Fatigue Scale (52), which yields three scores for general fatigue, cognitive fatigue, and sleep-rest fatigue. It has been widely used in many pediatric chronic health conditions demonstrating strong reliability and validity. Global health will be assessed with the PROMIS pediatric global health measure (53), a 7-item measure summarizing a child's physical, mental, and social health into a single score. Concurrent validity has been recently demonstrated with lower scores for children with chronic conditions and strong relationships with measures of positive health.

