
**Treatment engagement, adherence, and acceptability.** Treatment engagement will be measured by completion of at least 1 module while adherence is defined as the completion of 6 or more modules. The administrative interface of the WebMAP program has a tracking system in place for recording each time a user logs onto the program. Each module contains multiple-choice quizzes concerning the content presented as well as behavioral assignments, fill-in-the-blank fields, and use of the diary tracker. Data fields completed within modules are stored, generating a comprehensive activity record of module specific use including self-management tasks. Treatment acceptability and satisfaction will be assessed with the Treatment Evaluation Inventory (54), which we have adapted for pain self-management, and ratings of global

impression of change.

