### 9.3 Statistical Analyses

Data will be reviewed for completeness and errors including consistency checks for relevant variables. Tabular and graphical methods of data exploration including frequency tables, scatterplots, and box plots will be used to explore distributions of study variables. For the primary analytic plan, we will rely

on panel and latent growth models (LGM), within the structural equation modeling (SEM) framework (55-57). Both approaches can be implemented within a manifest and/or latent variable context (58). Unlike traditional repeated-measures analysis of variance, SEM allows for a more accurate and flexible approach to analyzing repeated measures data by simultaneously modeling change in the means (fixed effects) and in the variance and covariance of initial level and change (random effects) (56, 59-61). We include biological covariates of age, sex, and pain location in all models. We expect 10% attrition for a final projected sample size of  $n = 72$ . Full Information Maximum Likelihood (FIML) estimation will be used to handle missing data related to attrition and non-response (62) incorporating robust standard errors or bootstrapping to correct for non-normality (61). FIML estimation improves accuracy and power relative to other missing data handling methods (63, 64).

**Aim 1. Characterize the relationship between baseline sleep deficiency and self-management processes.** We will use structural equations (65, 66) to assess interrelations, direct effects, and indirect mediation effects in a longitudinal panel model. Mediation will be tested by decomposing a total effect of each sleep deficiency measure (duration, wake time, quality, insomnia symptoms) on self-management processes into direct effects and indirect effects (65, 66). Significance tests of indirect effects will be carried out using the Monte Carlo (*empirical-M*) method to obtain 90% asymmetric confidence intervals (67-69).

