Expected Results, Interpretation, and Possible Pitfalls. We expect the higher the level of sleep deficiency the higher negative affect, lower positive affect, *lower executive functioning*, lower the behavioral activation, self-efficacy, and self-regulation at baseline. There will likely be an indirect effect of sleep deficiency on affect *and executive function* and of affect *and executive function* on self-management processes. *We also expect that a significant indirect effect will indicate that sleep deficiency affects change in self-management processes by influencing affect or executive function.*

**Aim 2. Determine the effect of baseline sleep deficiency on treatment acceptability, engagement with, and benefit from an internet-delivered pain self-management intervention.** We will use LGMs to model individual differences in final acceptability and engagement status and the rates of change in global health, pain symptoms, fatigue, and pain-related disability (56, 59-61) and to test the proposed predictive and mediated effects.

Expected Results, Interpretation, and Possible Pitfalls. We expect that global health will improve over the course of the study while pain, fatigue, and pain-related disability will decrease. We also expect that participants will significantly vary around the average intercept and slope. We expect the higher the initial level of sleep deficiency the shallower the increase in global health over time and the shallower the decline in pain, fatigue, and pain-related disability. Across all models we expect less than 10% attrition over the course of the study based on our prior work (27). We will use the maximum likelihood estimation option in the Mplus 7.3 software program to deal with missing data and use the robust standard error option to correct for non-normality (61).

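### Section 9.3 names no auxiliary variable for FIML; adding modules completed would make missing at random more plausible, chiefly for the web-hosted pain and CALI diaries, at almost no cost

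*Combined protocol and SAP*

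**What the plan says.** Section 9.3 (Statistical Analyses) states: "Full Information Maximum Likelihood (FIML) estimation will be used to handle missing data related to attrition and non-response". On covariates it says: "We include biological covariates of age, sex, and pain location in all models". Sections 9.2 and 9.3 mention no auxiliary variable, do not state a missing-at-random assumption, and plan no sensitivity analysis for departures from it.

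On the amount of missing data, Section 9.3 gives "We expect 10% attrition for a final projected sample size of" 72, and later "Across all models we expect less than 10% attrition over the course of the study based on our prior work". Section 5.5 sets enrolment at 80.

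On where outcomes are collected, Section 8.1 says "WebMAP has diary assessments programmed into the web site to prospectively collect pain intensity and pain-related disability data over 7-day periods". The same section places all questionnaires in REDCap. These include the three self-management measures of H1, and fatigue and global health from H4.

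On engagement, Section 8.1 describes a system for "recording each time a user logs onto the program" and stores module-level activity. Section 6.3 adds that lesson completion is documented and makes modules completed the primary adherence measure. In Sections 9.1 and 9.3 engagement appears as an Aim 2 outcome, which H3 expects to be lower with greater sleep deficiency. It is given no role in handling missing data.

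**The concern.** FIML protects against missingness that is explained by variables in the model. If response depends on something outside the model that is also related to the outcome, the estimate is biased.

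Engagement is a natural candidate. It is observed even when outcomes are not, since a youth who never logs on has a known count of zero modules. The trial itself hypothesises that it depends on the exposure. Two of the H4 outcomes, pain intensity and CALI, are completed on the site that a disengaged youth has stopped visiting. For the REDCap questionnaires the link is less direct: a youth may abandon the programme and still answer an emailed survey.

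At stake is the size of the sleep association in H4 and, less directly, in H1. The data that would make the assumption more credible are already stored.

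**Working it through.** **The plan's own figure.** 80 × (1 − 0.10) = 72, which reproduces the projected final sample.

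**Inputs**
- From the documents: R² = .06 for the slope (Section 9.2). In SD units the sleep effect on change is −√.06 = −0.245. Missingness of 10% is from Section 9.3.
- Assumed, since the documents give no values: correlation of engagement E with sleep deficiency X, −0.3 to −0.5; correlation of E with change Y given X, 0.3 to 0.5; log-odds of a missing outcome per SD lower engagement, 1 to 2; missingness of 5% to 30%.
- Why look above 10%: Section 8.1 reports prior compliance of over 85% for at least 5 of 7 diary days. If that shortfall were wholly separate from 10% attrition, incomplete diary data could reach 1 − 0.90 × 0.85 = 23.5%. This is an upper illustration. The figure is for sleep diaries, may overlap attrition, and partial weeks can still be averaged.

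**Formula.** Let b_X and b_E be the coefficients of Y on X and E. Let a be the slope of E on X in everyone, and a_obs the slope in those with Y observed.
- FIML with E as auxiliary estimates b_X + b_E × a, the total sleep effect.
- FIML without E estimates b_X + b_E × a_obs.
- Bias = b_E × (a_obs − a).

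Losing low engagers flattens the negative slope of E on X, so a_obs − a is positive. The sign of the bias is then the sign of b_E. If b_E is positive, −0.245 moves toward zero; if b_E is negative, it moves away from zero by the same amount.

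**One case in numbers** (correlations −0.3 and 0.5, log-odds 2, 10% missing). b_E = √(1 − .06) × 0.5 / √(1 − 0.3²) = 0.970 × 0.5 / 0.954 = 0.508. The simulated bias is 0.022, so a_obs − a = 0.022 / 0.508 = 0.043: the slope of E on X flattens from −0.300 to about −0.257. Relative bias is 9.1%.

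**Large-sample results over the assumed range** (1,000,000 records per scenario, positive b_E):

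| Missing | Sleep effect shrinks by | Mean change overstated by (SD) |
|---|---|---|
| 5% | 1.5% to 9.3% | 0.015 to 0.036 |
| 10% | 3.0% to 14.1% | 0.026 to 0.068 |
| 20% | 4.0% to 21.9% | 0.048 to 0.125 |
| 30% | 5.8% to 28.5% | 0.071 to 0.181 |

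With E as auxiliary the residual bias is within 0.003 SD throughout. With a weaker sleep–engagement correlation of −0.25, engagement effects of 0.3 to 0.5 and log-odds 1, shrinkage at 10% missing is 2.2% to 3.4%. That gives the lower end of the 2% to 14% range.

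**At N = 80** (3,000 replicates, correlations −0.3 and 0.5, log-odds 2):
- 10% missing: mean estimate −0.223 without E and −0.245 with it; sampling SD 0.115 either way. Bias / SD = 0.022 / 0.115 = 0.19.
- 30% missing: −0.204 and −0.247; sampling SD 0.131 and 0.132. Bias / SD = 0.041 / 0.131 = 0.31.

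Replacing E by a bounded count of 0 to 8 modules still removed nearly all of the bias, with the sampling SD at 10% missing about .11 to .12 either way.

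**What this leaves out.** The model above has a single change score. A growth model also uses earlier outcomes. With an assumed residual correlation of .6 between the post-treatment and 6-month scores, and the former observed in half of those missing the latter, the 2.2% to 3.4% shrinkage falls to 1.6% to 2.0%.

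**The case against.** The strongest reply is that the plan already separates assessment from programme use. Youth are paid $40 per assessment and nothing for the intervention, and surveys and diaries have their own reminders (Section 5.5). Staff pursue non-completers (Section 7.3). Section 8.2 aims for complete data on more than 95% of retained subjects and tracks reasons for missing data. This stands as a reason to expect little missing data. It does not make what remains independent of engagement.

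Four stronger readings are tempting, and the documents do not support them.
- *That all missing outcomes share this mechanism.* Only pain intensity and CALI are on the WebMAP site; the H1 measures, fatigue and global health are in REDCap.
- *That non-response will follow disengagement and is therefore non-ignorable.* No passage says so. It is a reasonable inference, and bias also needs engagement to predict benefit given everything else in the model. The mediation models include affect and executive function, which may absorb part of that link.
- *That the plan excludes engagement from the outcome models.* The Aim 2 text in Section 9.3 names engagement status and rates of change in one sentence on growth models, so a joint model is not ruled out. The gap is that no such role is stated.
- *That the bias must run toward zero.* If youth who feel better stop using the programme, it runs the other way. The documents give no estimate of the engagement–benefit relation.

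Any overstatement of mean improvement matters less here, because Section 4.2 says that efficacy is not the aim.

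**Conclusion.** The gap is real and its severity is low. Section 9.3 leaves out of its missing-data model a recorded variable that the trial itself ties to the exposure and that probably predicts diary non-response. Including it would make missing at random more plausible.

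At the planned 10% attrition the bias is roughly 2% to 14% of the sleep effect. That is about one fifth of a sampling SD in the N = 80 case worked through, and about 0.034 / 0.115 = 0.30 at the 14% extreme if the same SD applies. At 20% to 30% diary non-response it could reach 22% to 29% under the strongest assumed links. Every input except the effect size and the 10% is an assumption, the sign depends on whether low engagers improve less or more, and observed intermediate scores would reduce the bias.

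**What to change.** Add to Section 9.3: *Number of modules completed during the 8-week treatment phase will be included as an auxiliary (saturated-correlate) variable, not as a predictor, in the FIML models of pain intensity and CALI, and in the other H1 and H4 outcome models where the model converges.*

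It should not be a predictor because engagement may lie on the path from sleep to benefit, and adjusting for it would change the total effect being estimated. Raw login counts should not be used unless diary logins can be separated out: on a site that hosts the outcome diaries, a login count partly records response itself. If a joint model with engagement was already intended for Aim 2, the text should say so.

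The cost is one sentence and one more variable in models with about 72 completers, using data already stored and with almost no loss of precision.

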**Aim 1. Characterize the relationship between baseline sleep deficiency and self-management processes.** H1. Greater baseline sleep deficiency (shorter sleep duration, poorer sleep quality, increased insomnia symptoms, greater wake time after sleep onset) will be associated with lower activation, lower pain self-efficacy, and lower use of self-management skills from pre- to post-treatment. H2. Positive and negative affect and executive functioning will mediate the relationship between sleep deficiency and self-management processes.

**Aim 2. Determine the effect of baseline sleep deficiency on treatment acceptability, engagement, and benefit from an internet-delivered pain self-management intervention.** H3. Greater sleep deficiency will be associated with lower perceptions of treatment acceptability and engagement (fewer logins, fewer completed treatment modules and assignments). H4. Greater sleep deficiency will be associated with less benefit (fewer improvements) in ratings of global health, fatigue, pain symptoms, and pain-related disability following pain self-management intervention. H5. Positive and negative affect and executive functioning will mediate the relationship between sleep deficiency and treatment acceptability, engagement and benefit.

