### 6.3 Study Intervention/Experimental Manipulation Adherence

Treatment is consistently delivered via the web programs. Study staff ensure that each participant has downloaded and set up the intervention program within 7 days of completing the baseline assessment. The web programs track each time a parent or youth uses the program and document when lessons are completed. The primary measure of adherence will be the number of modules completed.

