## 8 STUDY ASSESSMENTS AND PROCEDURES

### 8 STUDY ASSESSMENTS AND PROCEDURES/EVALUATIONS

#### 8.1 Study Procedures/Evaluations

Assessments will occur at baseline ( $T_1$ ), immediately after intervention (2 months;  $T_2$ ), and repeated at 6 months ( $T_3$ ). Mediators will be assessed at an additional mid-treatment (4 weeks) data point. The intervention phase will last 2 months (8 weeks). All questionnaires will be administered using Research Electronic Data Capture (REDCap), a secure web-based tracking and on-line data acquisition system (40). We have used this system successfully in multiple studies to date. Estimated time burden is 10 minutes for parents and 40 minutes for teens. Response burden is minimized by the online administration, which allows saving and storing of responses.

**Screening Measures.** Participants will complete the Pediatric Sleep Questionnaire (41) to screen for sleep-disordered breathing. If they screen positive they will be referred for clinical evaluation and will not be enrolled. Parents will complete a Demographic Questionnaire to assess sociodemographic variables and pain history.

**Mediators.** Positive and negative affect will be assessed with the Positive and Negative Affect Scale-Child version (PANAS-C; (48). The PANAS-C consists of two mood scales with 10-items each rated on a 5-point scale for assessing positive (e.g., inspired, strong) and negative affect (e.g., guilty, scared). Both scales are internally consistent, uncorrelated, and stable over a 2-month time period; good convergent and discriminant validity have also been demonstrated (48). Executive functioning will be assessed with the Behavior Rating Inventory of Executive Function (BRIEF-2) (49), a short 12-item well validated self-report measure that assesses executive function behaviors (e.g., inhibitory control, working memory, planning and organization) in home and school environments providing three indices of regulation, Behavioral, Emotional, and Cognitive.

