### 9.2 Sample Size Determination

Aim 1: A series of Monte Carlo simulations were conducted to evaluate longitudinal mediation (70). Results indicate 80% power for a sample size of 75 given a mediated effect of approximately 27% or larger and specific indirect effects of  $R^2 = .12$  or larger.

Aim 2: A series of Monte Carlo simulations were specified (27) to evaluate power to detect variance in linear change. Results indicate a sample size of 52 is needed. Adding predictive structural paths to the simulated LGMs indicated that a sample size of  $N = 75$  would be powered at .80 to detect an effect size as small as  $R^2 = .06$  and .03 for the slope and intercept, respectively (71).

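### Aim 2 names a growth model for acceptability and engagement, for which no repeated measure is defined, and section 8.1 reduces engagement to a one-module yes/no that departs from H3

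*Combined protocol and SAP*

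**What the plan says.** Section 9.3 (Aim 2) gives one model family for all Aim 2 outcomes: "We will use LGMs to model individual differences in final acceptability and engagement status and the rates of change in global health", followed by the other health and pain outcomes. The general part of 9.3 places the work in panel and growth models within SEM, with manifest or latent variables, full-information maximum likelihood and robust standard errors. It adds: "We include biological covariates of age, sex, and pain location in all models".

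Engagement appears in two forms:
- H3 (sections 2.1 and 9.1, same wording): "engagement (fewer logins, fewer completed treatment modules and assignments".
- Section 8.1: "Treatment engagement will be measured by completion of at least 1 module while adherence is defined as the completion of 6 or more modules".

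Section 6.3 adds: "The primary measure of adherence will be the number of modules completed". Section 8.1 also describes "a tracking system in place for recording each time a user logs onto the program" and says that the fields completed within modules are stored.

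For H4, the form of change is named only in 9.2, where simulations were run "to evaluate power to detect variance in linear change". Section 9.3 speaks of an average intercept and slope but gives no time scores. Section 8.1 sets the assessments at baseline and 2 months, "and repeated at 6 months". The synopsis (1.1) has 10 weeks and 6 months, and section 8.2 has 3 months after the intervention.

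**The concern.** A growth model describes change over repeated occasions. The word final, and the lack of any repeat schedule, suggest one value per youth for acceptability and for engagement. The schedule of activities (1.3) has no row for either, and the endpoint table in section 3 lists only pain intensity and activity limitation under the Aim 2 objective. H3, and the part of H5 that concerns acceptability and engagement, are therefore left without a stated model that fits their outcomes, and the analyst would have to choose one.

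The two forms of engagement differ in kind: three quantities in H3, a yes/no in 8.1. Most youth who receive access and set-up help will probably finish at least one module, so the yes/no would carry little information about the effect of sleep.

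**Working it through.** **Plan figures.** Section 9.3 projects 80 × (1 − 0.10) = 72, which reproduces. The Aim 2 power statement in 9.2 concerns the slope and intercept of a growth model. H3 has no power figure of its own to reproduce.

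**Can the named model be fitted?** A linear growth model on w occasions has w means plus w(w+1)/2 variances and covariances to work from. It estimates 2 factor means, 2 factor variances, 1 factor covariance and w residual variances, so 5 + w parameters.

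| Occasions | Moments | Parameters | df |
|---|---|---|---|
| 1 | 1 + 1 = 2 | 6 | −4 |
| 2 | 2 + 3 = 5 | 7 | −2 |
| 3 | 3 + 6 = 9 | 8 | +1 |

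The H4 outcomes, with three occasions, can be fitted. A single end value cannot.

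**What the one-module rule would cost.** Inputs from the documents: n=72 (9.3), eight modules (6.1), covariates age, sex and pain location (9.3). Assumed: 90% to 95% of youth complete at least one module, 30% to 60% complete all eight, counts 1 to 7 are equally likely, engagement follows an underlying normal variable correlated √R² with sleep, and tests are two-sided at .05.

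Expected number scoring no: 72 × 0.10 = 7.2, or 72 × 0.05 = 3.6. Taking three pain locations, the model has five predictor terms: sleep, age, sex and two location indicators.

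Simulated power:

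| Outcome | R²=.10 | R²=.06 |
|---|---|---|
| At least 1 module (yes/no) | 25-36% | 15-24% |
| At least 6 modules (yes/no) | 52-59% | 34-38% |
| Modules completed (0-8) | 58-71% | 38-48% |

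Repeat runs with other tests of the same outcomes moved these ranges by up to about five points and did not change the order.

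**Which model for the count?** With the covariates and robust errors, linear regression on the 0-8 count had power of 56-68% (R²=.10) and 36-45% (R²=.06), with type I error of 3.9% to 4.9%. Ordered probit had 62-73% and 44-53%, but its type I error was 5.3% to 7.7%, so part of its advantage may be inflation of test size. The linear model that the plan already allows is adequate.

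**Do the differing visit times matter for H4?** Section 8.2's follow-up falls at about month 2 + 3 = 5. With the last visit scored 1, the middle visit scores 2/6 = .33 (8.1), 10/26 weeks = .38 (1.1) or 2/5 = .40 (8.2). Centred, the two extreme codings are (−.444, −.111, .556) and (−.467, −.067, .533). Their correlation is .511/√(.519 × .507) = .997. If change is truly linear, using the wrong one of the three changes power by less than 0.2 points (n=72, R²=.10, assumed change SD 0.6, residual variance 0.1 to 0.6).

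**The case against.** The best defence is that 9.3 is broader than its Aim 2 sentence. SEM with manifest variables and robust errors includes ordinary regression, so H3 can be analysed within the declared framework. That stands, and a reader who infers that H3 cannot be analysed at all goes too far. What is missing is a statement of the model. Reading final status as an intercept centred at the last visit does not fill the gap, because it still needs repeated measures. The login log could supply a weekly series, but the plan does not define one.

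Second, 9.1 is the hypothesis section and names the three quantities, so an analyst may follow it and never use the one-module rule. That also stands: the power loss arises only if the 8.1 rule is applied to H3.

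Third, a reader might infer that adherence is defined inconsistently. A module count (6.3) and a 6-module cut-off of that count (8.1) can coexist; the plan need only say which is analysed.

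Fourth, a reader might infer that the missing H4 time coding puts the slope tests at serious risk. Sections 9.2 and 9.3 together point to one linear slope, and the three visit schedules give almost the same slope weights. A large loss appears only under assumed non-linear trajectories, for which the documents give no basis.

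**Conclusion.** The concern holds in two parts. The model named for acceptability and engagement cannot be fitted to single end values, and no alternative is stated for H3 or the matching part of H5. The engagement rule in 8.1 conflicts with H3 and, if used, would cut power at R²=.10 from 58-71% to about 25-36%, and at R²=.06 from 38-48% to about 15-24%. The identification result is arithmetic. The power figures rest on assumed completion rates and an assumed distribution of modules, and the size of the loss depends on how many youth complete no module.

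The H4 time scores and visit times are a minor matter of consistency. The documents do not support a claim that H3 is untestable, or that the trial as planned is bound to lose this power. Nor do they make an ordinal or count model mandatory for every engagement outcome. The point concerns Aim 2, which 9.1 lists as the secondary objective, and it should be corrected before analysis.

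**What to change.** 1. **Section 9.3, H3.** Replace the growth model with a regression, within the SEM framework, of each end value on baseline sleep, age, sex and pain location. Use the linear model with robust errors for acceptability and the 0-8 module count, an ordinal model for the count as a sensitivity analysis, and a model suited to counts for logins.
2. **Section 8.1.** Define H3 engagement by the three measures in H3, with modules completed (0-8) as the lead one. Keep the 1-module and 6-module thresholds as descriptive summaries.
3. **Section 9.3, matching part of H5.** Use the same outcome models, with the indirect effect as the product a×b and the Monte Carlo interval already described for Aim 1. The week-4 mediator assessment falls inside the 8-week period in which modules accrue, so keep the time order, for example by counting only modules completed after that assessment. The downside is a narrower count: at one module a week, about 8 − 4 = 4 modules remain for a youth on schedule.
4. **Minor.** Reconcile the visit times in 1.1, 8.1 and 8.2, and state the H4 time scores.

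The cost is wording and a little analysis work. Modules, logins and assignment fields are already logged, so no data or visits are added.
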